6.5.2 Prohibited Medicines

Additional concurrent chronic systemic immune treatment, chemotherapy, radiotherapy (except the situation described in Section 6.5.1), hormone treatment for treatment of cancer (other than corticosteroids as antiemetic treatment and gestagens for tumor cachexia which are allowed) or any other investigational agent may not be administered to subjects in this trial.

Any traditional Chinese medication with approval for use as anticancer treatment (regardless of the type of cancer) will not be permitted. Traditional Chinese medication for indications other than anticancer treatment, such as supportive care, may be administered at the discretion of the Investigator.

If the administration of a nonpermitted concomitant drug becomes necessary during the trial, e.g., for AEs or in an urgent medical situation, it is at the Investigator's discretion. In such a case, this subject has to be withdrawn from trial treatment and detailed information needs be recorded.

6.5.3 Other Trial Considerations

After the end of the trial, all subjects will receive further treatment based on local medical practice.

6.5.4 Special Precautions

Subjects enrolled in this clinical trial will be provided with an Emergency Medical Support Card during their trial participation. The Emergency Medical Support Card, which will be provided by the Sponsor, is based on the need to provide clinical trial subjects with a way of identifying themselves as participating in a clinical trial, and subsequently to provide any health care provider with access to the necessary information about their participation. This may be needed to determine the course of the subject's medical treatment. This service is designed to provide information to health care providers who are not part of the clinical trial. Clinical Trial Investigators, who are already aware of the protocol and treatment, have other means of accessing necessary medical information for the management of emergencies occurring in their subjects.

The first point of contact for all emergency situations will be the Clinical Trial Investigator caring for the affected subject. The Investigator agrees to provide emergency contact information on the Emergency Medical Support Card for this purpose. If the Investigator is available when an event occurs, she/he will answer the question.

6.6 Packaging and Labeling of the Investigational Medicinal Product

The packaging, labeling, and documentation of the cetuximab will be in accordance with applicable local regulatory requirements and applicable GMP Guidelines, so that it shall be possible to retrace the composition and pharmaceutical quality. All labels are given in the Trial File.

6.7 Preparation, Handling and Storage of the Investigational Medicinal Product

Instructions for the handling and preparation of the cetuximab solution for infusion will be provided.

All cetuximab treatment boxes supplied to each trial center must be stored carefully, safely, and separately from other drugs. Cetuximab should be stored in a refrigerator at 2° to 8°C until use, with a temperature log maintained daily.

The IMP must not be used for any purpose other than the trial. The administration of IMP to subjects who have not been enrolled into the trial is not covered by the trial insurance for subjects.

The Investigator (or the pharmacist or another person who is designated by the Investigator) will maintain the following records for the IMP:

- Receipt of treatment boxes at the trial center.
- Inventory at the center.

- Administration to each subject.
- Destruction of unused IMPs.

It must be ensured that the IMPs are not used at each trial center:

- After the expiry date, or
- After the retest date unless the IMP is reanalyzed and its release date extended.

This is to be closely monitored by the trial monitor and trial manager.

Upon completion or termination of the trial, the Investigator/pharmacist will destroy all unused IMPs after approval by the monitor. The Investigator/pharmacist will provide the local monitor with a copy of the inventory record for filing and a record of the used, unused and destroyed clinical supplies, to facilitate inventory procedures. This form shall include information on:

- All administered units.
- All unused units.
- All units destroyed at the end of the trial.
- Date of destruction.
- Name and signature of the Investigator/pharmacist.

6.8 Investigational Medicinal Product Accountability

The Investigator (or designee) is responsible for ensuring IMP accountability, including reconciliation of drugs and maintenance of records.

- Upon receipt of IMP, the responsible person will check for accurate delivery and acknowledge receipt by signing or initialing and dating the appropriate documentation and returning it to the location specified. A copy will be archived for the Investigator Site File.
- IMP dispensing will be carefully recorded on the appropriate drug accountability forms so that accurate records will be available for verification at each monitoring visit.
- Trial center IMP accountability records will include the following:
 - Confirmation of IMP receipt, in good condition and in the defined temperature range.
 - o The inventory of IMP provided for the clinical trial and prepared at the center.
 - o The use of each dose by each subject.
 - o The disposition (including return, if applicable) of any unused IMP.
 - O Dates, quantities, batch numbers, vial numbers, expiry dates, formulation (for IMP prepared at the center), and the individual subject trial numbers.

China First-line Head and Neck Trial (CHANGE2)

The Investigator center should maintain records, which adequately document that subjects were provided the doses specified in this protocol, and all IMPs provided were fully reconciled.

Unused IMP must not be discarded or used for any purpose other than the present trial. No IMP that is dispensed to a subject may be redispensed to a different subject.

A Trial Monitor will periodically collect the IMP accountability forms and will check all returns (both unused and used containers) before arranging for their return to the Sponsor or authorizing their destruction by the trial center, or following the local hospital medical waste destruction practice for used containers.

6.9 Assessment of Investigational Medicinal Product Compliance

Cetuximab treatment and chemotherapy will be administered either by the Investigator or under his or her supervision in an inpatient setting.

The application dates and exact amounts of cetuximab, cisplatin, carboplatin, and 5-FU given at each infusion will be documented in the eCRF. If cetuximab and/or cisplatin and/or carboplatin and/or 5-FU treatment is interrupted during the actual infusion, the clinical staff will estimate the percentage of the dose received by the subject and document it in the eCRF.

Any reason for noncompliance should also be documented. Insufficient compliance is defined as a subject missing > 2 consecutive infusions of cetuximab or > 21 consecutive days chemotherapy infusion delay for nonmedical reasons. In the event of insufficient compliance, discontinuation of the trial treatment will be considered in mutual agreement between the Investigator and Sponsor on a case-by-case basis.

The IMP administration must be recorded in the eCRF.

6.10 Blinding

This trial will be an open-label trial as most subjects treated with cetuximab will experience skin reactions, facilitating their identification.

6.11 Emergency Unblinding

Not applicable.

6.12 Treatment of Overdose

CCI

An overdose is defined as any dose greater than the highest daily dose included in a clinical trial protocol or planned for an individual subject enrolled in the trial (\leq 5% more than planned dose will not be considered as overdose). Even if it does not meet other criteria for an SAE, any overdose

must be recorded in the trial medication section of the CRF and reported to Drug Safety in an expedited manner using the SAE Report Form, and following the procedure in Section 7.4. To date, there is limited experience with single cetuximab doses higher than 400 mg/m² BSA or weekly administrations of cetuximab doses higher than 250 mg/m² BSA. In clinical studies with cetuximab doses up to 700 mg/m² given every 2 weeks, the safety profile was consistent with that described in Section 3.7.4. Any drug overdose (>10% of calculated dose per plan) occurring in the present trial must be reported as an SAE (see Section 7.4.1.4).

In the case of overdose of chemotherapy/cetuximab, the Investigator should provide all possible medical care and treatment in accordance with local medical practice.

6.13 Medical Care of Subjects after End of Trial

After a subject has completed the trial or has withdrawn early, usual treatment will be administered, if required, in accordance with the trial center's standard of care and generally accepted medical practice and depending on the subject's individual medical needs. The Sponsor will provide trial treatment for free if the Investigator considers the subject is benefiting from it, until cetuximab is approved and marketed in China for the indication of SCCHN.

7 Trial Procedures and Assessments

7.1 Schedule of Assessments

Before performing any trial assessments that are not part of routine medical care for the subject, the Investigator will obtain written informed consent as described in Section 9.2.

This section summarizes the types of assessment to be performed by visit type. A complete schedule of assessments is given in Table 1.1.

The trial will be terminated when the last subject has discontinued the trial treatment or OS cut-off, whichever is later. After OS cut-off and before the trial termination, only SAEs during treatment and at the EOEA visit will be reported, following the usual reporting procedure. Information collected in the EOEA forms will be limited to data on date of trial treatment completion, date of last treatment, subject status at end of trial, reason for discontinuation, disease progression (yes/no). From alive, but trial-treatment-discontinued subjects, no tumor response data, anti-cancer treatment and survival information will be collected.

7.1.1 Screening Visit

The screening visit (baseline) must take place in the 28 days before the start of trial treatment.

The following tests and procedures will be performed at this visit:

• Written informed consent.

- Primary tumor diagnosis (see Section 7.2.2).
- Documentation of AEs starting from the date of first signature of informed consent.
- Documentation of demographic data, height, and relevant medical history (see Section 7.2.3).
- Documentation of prior and concomitant medications (see Section 6.5).
- Check of inclusion and exclusion criteria (see Section 5.3).
- Physical examination, check of vital signs, and assessment of ECOG performance status (see Section 7.4.4).
- ECG (to be repeated if performed more than 7 days before the first dose of trial treatment) (see Section 7.4.4.4).
- Blood samples collected after fasting for at least 8 hours for safety laboratory assessments (hematology and biochemistry [see Section 7.4.3]), and to be repeated if performed more than 7 days before the first dose of trial treatment.
- Urinalysis (to be repeated if performed more than 7 days before the first dose of trial treatment) (see Section 7.4.3).
- If calculated creatinine clearance is <60 mL/min, 24 hour creatinine clearance might be requested by the Investigator for confirmation (see Sections 7.1 and 7.2.7).
- Serum pregnancy test (if applicable) (see Section 7.2.5).
- HBV antigen and antibody test, HCV antibody test, and HIV test (see Section 7.2.4).
- Collect HPV, tobacco, and alcohol consumptions status (if the subjects has done HPV test before the screening, the HPV data should be collected. Tobacco and alcohol consumptions status should also be documented) (see Section 7.1).
- Echocardiogram (see Section 7.2.6).
- Tumor assessment (see Section 7.3).

7.1.2 Weekly Cetuximab Administration Visit

For subjects in Arm A, the following procedures and investigations will be performed at weekly intervals (\pm 3 days) until the last dose of cetuximab:

- Physical examination (see Section 7.4.4).
- Check of vital signs.

Document No. CCI
Object No.

- Documentation of AEs and concomitant medications.
- Administration of cetuximab (based on BSA).

7.1.3 Start of Each Cycle Visit (Day 1 of Each 21-Day Cycle)

For all subjects in Arm A and B, the following procedures and investigations will be performed on Day 1 of each 21-day chemotherapy cycle. A visit window of 3 days is acceptable.

- Randomization (for Cycle 1 only, see Section 6.3).
- Physical examination, check of vital signs, and assessment of ECOG performance status (see Section 7.4.4).
- ECG (see Section 7.4.4.4).
- Blood samples collected after fasting for at least 8 hours for safety laboratory assessments (within 3 days before start of next cycle) (see Section 7.4.3).
- Urinalysis (within 3 days before start of next cycle) (see Section 7.4.3).
- Documentation of AEs and concomitant medications.
- Administration of cetuximab (based on BSA) only for subjects in Arm A.
- Administration of cisplatin (cisplatin may be replaced by carboplatin in subsequent cycles if there are cisplatin-related nonhematologic toxicities) and 5-FU (based on BSA) for subjects in Arm A and B.

Note: ECG and laboratory safety results must be available at start of each cycle visit.

Note: If the subject is not able to visit the Investigator for this evaluation or misses the scheduled visits, the Investigator should attempt to contact the subject or the referring physician by appropriate means to determine the subject's well-being.

7.1.4 6-Weekly Evaluation Visit

For all subjects in Arm A and B, the following procedures and investigations will be performed at 6-week intervals starting from the first dose of trial treatment until the EOEA. A visit window of 3 days is acceptable.

- The evaluations which are completed within 7 days at 6-weekly evaluation visit for physical examination/weight; vital sign; ECG; hematology; biochemistry, and urinalysis can be accepted, and these evaluations at 6-weely evaluation visit will be optional.
- Assessment of ECOG performance status (see Section 7.4.4).
- Documentation of AEs and concomitant medications.
- Tumor assessment (see Section 7.3).

7.1.5 End of Efficacy Assessment Visit

Subjects are to attend the EOEA visit on the day of the last efficacy assessment. A visit window of 3 days is acceptable. The following procedure and investigations will be performed:

- Physical examination, check of vital signs, and assessment of ECOG performance status (see Section 7.4.4).
- ECG (see Section 7.4.4.4)*.
- Blood samples collected after fasting for at least 8 hours for safety laboratory assessments (see Section 7.4.3)*.
- Urinalysis (see Section 7.4.3)*.
- Documentation of AEs and concomitant medications.
- Tumor assessment (see Section 7.3).

*If the EOEA Visit is after the safety follow-up visit, these tests are optional.

7.1.6 Safety Follow-Up Visit

Subjects are to attend the Safety Follow-up visit 30 days (\pm 3 days) after the last dose of trial treatment or immediately before commencing the start of any new anticancer treatment (see Section 6.5.3 for details). The planned procedures and investigations, except tumor assessment, are the same as the EOEA visit (see Section 7.1.5).

7.1.7 Survival Follow-Up

The following assessments will be performed every 3 months after the EOEA visit until death or termination of the trial, whichever comes first. This follow-up can take the form of a telephone contact to the subject or the subject's family, or their referring doctor.

- Survival status.
- Documentation of subsequent antitumor treatment after the end of trial treatment.
- Outcome and resolution date of skin reactions.
- Resolution of ongoing SAEs (see Section 7.4.1.6).

Document No. CCI
Object No.

7.2 Demographic and Other Baseline Characteristics

7.2.1 Demographic Data

At screening, the following demographic data will be collected: date of birth, sex, and ethnic origin data

7.2.2 Diagnosis of Tumor

At the screening visit, the following data will be recorded for the tumor:

- Date of initial diagnosis and date of recurrence and/or metastasis.
- Histology.
- Localization.
- Recurrence or metastasis.
- Classification at initial diagnosis, according to TNM staging system, version 7, 2009.

7.2.3 Medical History

The following medical history data will be documented:

- Relevant previous and concomitant disease(s), other than SCCHN.
- Previous treatment for SCCHN.

7.2.4 Viral Serology

The antigen and antibody test for HBV, antibody test for HCV, and HIV test will be performed if clinically indicated. Subjects with known and declared HIV infection, as well as subjects with an active HBV or HCV infection resulting in an impaired liver function or cirrhosis will be excluded from the trial. These subjects will be identified during screening by either elevation of serum transaminases (i.e., not meeting inclusion criteria 8 for enrollment) (Section 5.3.1) and/or by the presence of a combination of markers of liver fibrosis (e.g., clinical, laboratory abnormalities, serologic markers, radiologic). Chronic asymptomatic HBV/HCV carriers are permitted into the trial.

7.2.5 Pregnancy Testing and Contraception

All female subjects of childbearing potential must have a negative blood pregnancy test at screening, which should be done within 7 days before the initiation of the trial treatment. Pregnancy testing must be repeated regularly throughout the trial if required by local legislation. All subjects, male or female, must practice medically-accepted contraception throughout the trial

if the risk of conception exists. The Investigator will decide together with the subject on adequate methods of contraception.

7.2.6 Echocardiogram

The left ventricular ejection fraction will be measured at screening by echocardiogram. Subjects with left ventricular ejection fraction less than 45% will be excluded from the trial.

7.2.7 Creatinine Clearance

The creatinine clearance will be calculated by trial centers based on serum creatinine according to local practices. Subjects with creatinine clearance less than 60 mL/minute will be excluded from the trial (24-hour creatinine clearance might be requested by the Investigator for confirmation, if calculated creatinine clearance is <60 mL/min).

7.2.8 Other Baseline Assessments

Other baseline assessments include physical examination, measurement of vital signs, assessment of ECOG performance status, ECG, CT or MRI of the brain (only if clinically indicated), neck, chest, and abdomen, safety laboratory assessments (hematology, clinical chemistry, electrolytes, urinalysis).

As these assessments are also performed at subsequent visits during the trial, refer to the relevant subsections of Sections 7.3 and 7.4 below for details of any method to be used.

7.3 Efficacy Assessment

7.3.1 Documentation of Tumor Assessments

A CT or MRI with contrast enhancement is recommended for tumor assessment.

Imaging, including CT or MRI of the brain (only if clinically indicated), neck (base skull to clavicles), chest, and abdomen, must be performed at baseline in order to review potential metastasis (≤28 days before trial treatment is acceptable). A bone scan and/or positron emission tomography (PET) scan should be considered for subjects who have possible bone metastasis at baseline or if bone metastasis is suspected during the trial; however, CT/MRI must be used for tumor assessment at baseline and at subsequent visits. The bone scan or PET cannot be used for measurement of target lesions.

At baseline, the organs with metastatic disease and the target and nontarget lesions should be documented. Evaluation of lesions should be performed at baseline and then every 6 weeks (\pm 3 days), regardless of any delays in trial treatment, until PD, as assessed by the Investigator. Tumor assessments should be conducted at each tumor assessment time point including a complete assessment of all target and nontarget lesions (see Table 1.1).

In the case of skin lesions, clinical evaluation should be made with a caliper and photos must be taken and made available.

All measurements should be recorded in metric notation.

Apart from trial center radiological reading to determine tumor responses, all images will also be assessed by an IRC. The IRC review will not interfere with the Investigator's judgment on tumor assessments.

Confirmation of progression needs to be based on radiological measurements. Clinical symptoms/signs suggestive of progression need radiological confirmation of PD. Subjects with a global deterioration of health status requiring discontinuation of treatment without radiological evidence of PD should be classified as "symptomatic deterioration". Any effort should be made to document the objective progression even after discontinuation of treatment (i.e., the subject needs to return for a final tumor assessment.

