Subjects in both arms will receive a maximum of 6 cycles of chemotherapy of 75 mg/m^2 cisplatin as intravenous infusion (refer to China package insert) on Day 1 of each 21-day treatment cycle, and then 750 mg/m^2 /day of 5-FU as a continuous intravenous infusion over 24 hours \pm 6 hours a day from Day 1 to Day 5 of each 21-day treatment cycle.

In the case of cisplatin-related nonhematologic toxicity, cisplatin may be replaced by carboplatin at a dose of target area under the serum concentration time curve of 5 in subsequent cycles. The decision needs to be made in discussion with the Medical Monitor on a case-by-case basis. Carboplatin will be administered using an intravenous infusion of 15 minutes or longer, and in accordance with the China package insert on Day 1 of each 21-day treatment cycle.

Planned treatment duration per subject:

The treatment duration per subject may vary. Subjects will be treated with a maximum of 6 cycles of chemotherapy and/or cetuximab weekly in the absence of PD, as assessed by the Investigator, and unacceptable toxicity. Subjects (in Arm A) who demonstrate at least a tumor response of stable disease (RECIST version 1.1) after 6 cycles of trial treatment will continue monotherapy with cetuximab until either PD or occurrence of unacceptable toxicity. Subjects who stop treatment before reaching PD will continue to have tumor assessments (CT or MRI) every 6 weeks until either PD, the start of a new antitumor treatment, death, or termination of the trial, or loss of follow up, whichever comes first. Upon occurrence of PD, all trial treatments should be discontinued.

Sample Size Calculation: CCI

Randomization: Randomization will be performed centrally using an interactive web response system (IWRS). A central stratified permuted block randomization procedure will be used to balance between treatment arms. The stratification factors are ECOG performance status (0 versus 1) and the primary tumor site (oral cavity versus hypopharynx versus others).

Statistical Analyses:

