**Censoring Rules**

| Situation                       |  | Date of event / censoring                           | Censoring |
|---------------------------------|--|---|-----------|
| Radiological PD (RECIST 1.1)    |  | Date of PD  | No        |
| No radiological PD (RECIST 1.1) | If death within 60 days after last tumor response assessment or the randomization (whichever is later) | Date of death (CRF)                                 | No        |
|                                 | If death not within 60 days after last tumor response assessment / No death                            | Date of last tumor response assessment within trial | Yes       |

Special cases which overrule general rules:

|  |   |                       |     |
|--|---|-----------------------|-----|
| No tumor assessment at baseline  | Death within 60 days after date of randomization                | Date of death         | No  |
|  | Death not within 60 days after date of randomization / No death | Date of randomization | Yes |
| No tumor assessment after start of treatment and no radiological PD (RECIST 1.1) | Death within 60 days after date of randomization                | Date of death         | No  |
|  | Death not within 60 days after date of randomization / No death | Date of randomization | Yes |

The last tumor assessment date is defined as the last available and evaluable tumor assessment performed prior to the cut-off date (or prior to EoS, i.e. subjects lost to follow-up or who withdraw consent). If no evaluable tumor assessment is available, this date will be the randomization date.

Imputation methods for estimating missing data:

- For imputing missing parts of dates for the efficacy analyses (except OS) the missing day in a date will be imputed as the 15th of the month, if month and year is documented. If the imputation is earlier than the date of randomization, the day of randomization is taken. In all other cases missing or incomplete dates will not be imputed.

- For imputing missing day of death date, if month and year is available, the day will be imputed by 15, unless this results in a date not later as a date the subject is known to be alive. In that case the date of death will be imputed by the last date known to be alive + 1.

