- Events: Radiological PD based on existing lesions (progressive disease reported for target and/or non-target lesions) / Radiological PD based on new lesions (new lesion(s) is/are reported) / Radiological PD based on existing and new lesions (both progressive disease reported for target and/or non-target lesions and new lesion(s) are reported) / Death within 60 days
- Censoring: Death not within 60 days / Censored at randomization / Lost to follow-up or withdraw consent / Due to data cut-off

Subjects will be considered as “censored at randomization” in case they have no tumor assessment at baseline and no tumor assessment after start of treatment and no radiological PD or death.

They will be considered as censored due to “Lost to follow-up/withdraw consent” in case they have no PD or death before they are lost to follow-up/withdraw consent.

They will be considered as censored “due to cut-off” in case they have no PD or death before the trial data cut-off.

A listing will display information on event and censoring including the following:

- Subject identification number,
- Treatment arm
- Randomization Date
- Last tumor assessment date before cut-off date
- Death date
- Progression date (IRC)
- PFS (IRC): Censoring Flag (Yes/No)/ Description of the Event/Censoring/ PFS (months)

A scatter plot will be produced to compare planned (y-axis) and actual (x-axis) relative day of tumor assessments by treatment arm (2 colors will be used to clearly identify treatment groups). The planned day for EOEA visit will be assigned as the planned day for the last available efficacy assessment visit.

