### 16.1.2 PFS Sensitivity Analyses

To assess the robustness of the primary analysis, the following analyses can be conducted:

- Per-protocol analysis: the same analysis as described above Section 16.1.1 will be repeated on PP analysis set only if PP analysis set includes less than 90% of the ITT analysis set.
- The same analysis as described above Section 16.1.1 will be repeated using results of the *clinical* review from IRC, corresponding listing will also be produced.
- The same analysis as described above Section 16.1.1 will be repeated considering all death as event.
- The same analysis as described above Section 16.1.1 will be repeated considering all death and start of new anti-cancer treatment as event.
- To address the bias due to different times of assessment of disease progression caused by different treatment schedules, the same analysis as described above Section 16.1.1 will be repeated considering date of planned imaging visits instead of date of actual imaging visits. If an event is observed between two planned visits, it will be assigned to the previous one. The planned day for EOEA visit will be assigned as the planned day for the last available efficacy assessment visit.
- The same analysis as described above Section 16.1.1 will be repeated excluding subjects who met the inclusion criteria 3 as defined in protocol version 1.0 (17 November 2014) but who do not meet the updated inclusion criteria 3 as defined in protocol version 2.0 (20 April 2016). Please refer to [Appendix 2](#) for the details for inclusion criteria 3.
- The same analysis as described above Section 16.1.1 will be repeated based on the stratification factors based on eCRF data instead of IWRS data.

Results of PFS primary and sensitivity analyses (hazard ratio and 95%CI) will be displayed using a forest plot.

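### Imaging stops at Investigator PD: the censoring table misclassifies subjects whose PD the IRC does not confirm, and no IRC-PFS analysis counts Investigator PD at its own date

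*Protocol*

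**What the plan says.** The primary endpoint is PFS by IRC in an open-label trial. Under Protocol 7.3.1, lesions are evaluated every 6 weeks "regardless of any delays in trial treatment, until PD, as assessed by the Investigator". The same section adds that "The IRC review will not interfere with the Investigator's judgment on tumor assessments", and the Protocol synopsis says that "Upon occurrence of PD, all trial treatments should be discontinued". No IRC confirmation before imaging stops, and no imaging after Investigator PD, is described. Protocol 5.1 also ends imaging at the start of a new antitumor treatment.

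For a subject without IRC PD, the Censoring Rules in SAP 16.1.1 count death within 60 days of the last assessment (or of randomization, if later) as an event. The remaining case, "If death not within 60 days after last tumor response assessment / No death", is censored at the last assessment. Two special cases are handled from randomization: no baseline assessment, or no assessment after the start of treatment. Either one alone is enough.

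A further table in 16.1.1 reports four censoring reasons by arm: death not within 60 days, censored at randomization, lost or withdrawn, and data cut-off. Subjects go under cut-off "in case they have no PD or death before the trial data cut-off". Censored at randomization is reserved for subjects with "no tumor assessment at baseline and no tumor assessment after start of treatment".

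SAP 16.1.2 repeats the IRC-PFS analysis with all deaths as events, and again "considering all death and start of new anti-cancer treatment as event". It also repeats it on the IRC clinical review. SAP 16.2.1 analyses Investigator PFS and tabulates IRC/Investigator concordance by arm, with a row for events seen by the Investigator only.

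**The concern.** Protocol 5.2 uses the IRC to guard against Investigator bias in an open-label trial. The Investigator's call nevertheless decides when the IRC's follow-up ends. A subject called progressed by the Investigator but not by the IRC is likely to be close to IRC progression, so censoring at that scan is informative. If such calls are more frequent in one arm, IRC events are lost selectively from that arm and the hazard ratio moves.

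The success rule offers no cushion. The trial is regarded as positive on a point estimate of 0.77 or less, without a hypothesis test. The table of censoring reasons is where a reader would look for this problem, and as defined it files some of these subjects as administratively censored.

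**Working it through.** **1. The plan's own figure.** EXTREME's PFS risk reduction is 46% (Protocol 3.7.2). Half of it retained on that scale gives 1 − 0.5 × 0.46 = 0.77, as stated. With 144 events and 2:1 allocation, SE(log HR) = 1/√(144 × 2/3 × 1/3) = 1/√32 = 0.177. At a true HR of 0.77, the chance of an estimate at or below 0.77 is therefore 0.50.

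**2. Rule against label, for subjects without IRC PD (SAP 16.1.1).**

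| Subject | Censoring rule | Reason in the table |
|---|---|---|
| Unconfirmed Investigator PD, death within 60 days | Event at death | Event; consistent |
| Unconfirmed, later death before cut-off | Censored at last assessment | Death not within 60 days |
| Unconfirmed, then lost or withdrawn | Censored at last assessment | Lost or withdrawn |
| Unconfirmed, alive and in follow-up | Censored at last assessment | Due to cut-off, although imaging ended earlier |
| Imaging stopped for new therapy, alive and in follow-up | Censored at last assessment | Due to cut-off, although imaging ended earlier |
| Baseline scan, no later scan, alive and in follow-up | Censored at randomization | Fails the table's definition, which needs both scans missing; falls under cut-off |

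If PD in the cut-off definition were read to include Investigator PD, the fourth row would fit no category.

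**3. Size, by simulation.** From the documents:
- 2:1 allocation, control median PFS 3.3 months and 6-weekly scans (± 3 days)
- cut-off at 144/240 = 60% IRC events
- the 60-day death rule
- median survival after PD of 5 months, borrowed from the PFS–OS gap in Protocol 5.2

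Assumptions not in the documents:
- A share q of subjects get Investigator PD one scan before the IRC would call it. This applies only where IRC PD would fall at the second scan or later.
- Half start new therapy 30 days after PD (range 30–70%).
- Accrual is uniform over 22 months, PFS is exponential and nobody is lost.

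Hazard ratios are from an unstratified Cox model on 300,000 subjects. The last column is from 2,000 trials of 240.

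| q, Arm A / Arm B | Primary | All deaths | Deaths + new therapy | Investigator PD as event | P(HR ≤ 0.77) |
|---|---|---|---|---|---|
| 0 / 0 | – | – | – | – | 0.49 |
| 20% / 20% | 0.765 | 0.774 | 0.771 | 0.770 | 0.53 |
| 30% / 10% | 0.702 | 0.713 | 0.750 | 0.814 | 0.70 |
| 10% / 30% | 0.834 | 0.838 | 0.795 | 0.732 | 0.34 |

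The true HR is 0.77 throughout. With q = 30%/10%, about 13% of all subjects had unconfirmed PD by cut-off; with 10%/30%, about 9%. At a true HR of 0.54, the two unequal cases give primary estimates of 0.488 and 0.589, both well inside 0.77. At a true HR of 0.65, P(HR ≤ 0.77) is 0.81 with no discordance, 0.95 with 30%/10% and 0.70 with 10%/30%.

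**4. Where the unconfirmed subjects end up.**
- 60-day deaths: 1 − 2^(−60/(5 × 30.4375)) = 0.24 by formula; about 23% in the simulation, where cut-off intervenes. These are primary events.
- Later deaths before cut-off: about 37–44%.
- Remainder labelled as cut-off: about 33–40% (100% less the 60–67% who die).
- The deaths + new-therapy analysis counts 76–82% of them (73–85% when uptake is varied), at a later date than the Investigator's call.

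**The case against.** Three stronger readings are tempting, and the documents support none of them.

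A reader might infer that no IRC-PFS analysis counts these subjects. SAP 16.1.2 has two that count those who die or start new therapy, which is most of them under the assumptions above.

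A reader might infer that all of them are reported as cut-off. Deaths within 60 days are events, and later deaths and losses have their own labels.

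A reader might infer that discordance is hidden. The concordance table in SAP 16.2.1 shows Investigator-only events by arm. Investigator PFS counts each such call at its date, so a wide gap between the two hazard ratios would be a warning.

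It is also fair to say that no document indicates different discordance by arm. The simulation further assumes that each unconfirmed call is exactly one scan early. If IRC progression would have come at more varied later times, the censoring would be less informative. The IRC charter, which might bear on this, is a separate document.

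Finally, counting Investigator PD overshoots: 0.81 and 0.73, against 0.75 and 0.80 from the planned deaths + new-therapy analysis, for a truth of 0.77. It also brings back the judgement that the IRC is meant to replace.

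All of this stands, and it limits the point without removing it. The concordance table gives counts, not the effect on the IRC hazard ratio. Investigator PFS changes the dates for everyone, so it does not isolate this group. In the unequal scenarios both planned IRC-PFS analyses fall on the same side of 0.77 as the primary result, and only the added analysis gives the opposite bound. The opening of 16.1.2 is also permissive about whether its analyses will be run.

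**Conclusion.** The point holds in limited form. Two parts rest on the text alone. The table of censoring reasons labels as cut-off some subjects whose imaging ended earlier, and its definition of censoring at randomization (both assessments missing) contradicts the Censoring Rules (either missing). The third part, that no planned IRC-PFS analysis counts Investigator PD at its own date, is also plain from SAP 16.1.2.

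The size of the bias is conditional. At a true HR of 0.77, an assumed 20-point difference in discordance between arms moves the primary HR to about 0.70 or 0.83. The chance of meeting the criterion moves from 0.49 to about 0.70 or 0.34. Equal rates move the HR by about 0.01. The documents do not show that bias exists or which way it would go. Because success rests on a bare point estimate, the change is worth making before the main analysis.

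**What to change.** 1. In the SAP 16.1.1 table of events and censoring:
   - Define censoring at randomization as in the Censoring Rules: baseline or post-baseline assessment missing.
   - Add two reasons, by arm: Investigator PD not confirmed by IRC, and new anti-cancer therapy.
   - Restrict the cut-off category to subjects still in scheduled imaging at cut-off.
   - State which reason takes precedence when a subject fits more than one.
2. In SAP 16.1.2, commit to one IRC-PFS sensitivity analysis in which subjects without IRC PD have an event at the date of Investigator PD. Present it beside the planned deaths + new-therapy analysis and describe it as an opposite bound, not as a corrected estimate.

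The cost is SAP wording and one further Cox run on data already collected. Imaging, treatment and the primary analysis are unchanged. The one drawback is that Investigator judgement enters IRC-PFS, in that sensitivity analysis only.
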